Comparison between Dorsal Root Ganglion Thermal Radiofrequency versus Pulsed Radiofrequency for the Management of Intractable Metastatic Pain in Thoracic Vertebral Body

Trial registration on Clinical Trial.gov: Clinical Trials

NCT03204942 on the 2nd of July 2017

Protocol date approval by National Cancer Institute (NCI)

Anaesthesia and Pain Management Department: 11 September 2016

NCI Cairo Ethics Committee approval: 14th of February 2017

Recruitment started: 30 July 2017

Recruitment Completed: 30 July 2018

Document Date (the date on which the uploaded document was most recently updated): 31 March 2019

INTRODUCTION

Metastatic disease to the bone has been a crippling devastating complication of various cancers, with unbearable pain ¹. Knowledge surrounding the pathophysiology of painful osseous metastases is rapidly changing ². Metastatic bone pain is characteristic of cancer pain and is a form of refractory cancer pain, as the pain includes not only nociceptive but also neuropathic pain that induces a peripheral and central sensitization.

The development of medication dose-limiting side effects, limits analgesic efficacy in nearly 42% of cancer pain patients ³.

In recent years the use of pulsed radiofrequency (PRF) to treat chronic pain conditions has generated intense interest in the pain community ⁴. PRF is a minimally invasive, target-selective technique that has reported benefit at reducing post-amputation stump pain, chronic radicular/ganglion pain , neuropathic pain , and arthropathic pain ^{5,6}.

In **2008**, **Zeldin** and **Ioscovich** published 3 cases of patients who suffered from uncontrolled vertebral/paravertebral metastatic pain and were successfully treated by fluoroscopically

guided selective dorsal root ganglion (DRG) PRF (PMG-230 Baylis Medical com. Inc. Canada) ⁷. They concluded that that PRF on selective DRG bilaterally under fluoroscopic guidance in patients with pain secondary to metastasis in the Thoracic vertebral body and who were unsuccessfully treated with opioids, may offer new opportunities for metastatic pain treatment and encourage future studies.

Another case series which was conducted by **Young-Chang P. Arai et al.**, in **2015** has concluded that DRG pulsed RF procedure provided sound pain relief for patients with intractable vertebral metastatic pain. PRF on DRG procedure provided sound pain relief for patients with intractable vertebral metastatic pain ⁸. Studies using animal models have clarified the anti-nociceptive effects of PRF on the DRG, it induces inhibition of excitatory c-fiber responses and a global reduction of evoked synaptic activity ^{9,10}. Several authors have reported that the anti-nociceptive actions induced by PRF would be due to the enhancement of noradrenergic and serotonergic descending pain inhibitory pathways and the inhibition of excitatory c-fibers ¹¹. It was found that the application of PRF to a DRG elicits the expression of c-fos in the dorsal horn ¹². The importance of this finding for the clinical effect of PRF is still a subject of discussion. C-fos is a specific marker indicating cellular activity¹³.

The alternative of modulation is clearly ablation, and in the vacuum that had persisted this possibility came up. The clinical effect of continuous radiofrequency treatment may therefore reflect a balance between analgesia produced by deafferentation-induced reduction in nociceptive input to the central nervous system and stimulation of pro-inflammatory, pro-nociceptive glial activation in the central nervous system as a consequence of deafferentation. Clinical experience indicates that analgesia is more commonly the result; however, central immune-mediated inflammation may predominate in patients who experience an increase in pain following the procedure ¹⁴. Thermal Radiofrequency (TRF) of the DRG was suggested as an alternative to ganglionectomy to destroy the primary afferents' soma. There is robust literature surrounding RF strategies to treat chronic pain, including treatment of the DRG. TRF uses high frequency electrical current, creating ionic oscillation of the tissue and frictional dissipation of the ionic current, producing heat ¹⁵.

Three prospective controlled trials have examined TRF-DRG for treating neuropathic pain stemming from cervical DRG. Van Kleef et al., 1996, Slappendel et al. , 1997 and Haspeslagh et al. , 2006. **Van Kleef et al.** performed a randomized, sham controlled, double blind study with cervicobrachialgia unresponsive to conventional therapy of 12 months duration and response to diagnostic selective nerve root blocks. In a double-blinded fashion, subjects were randomization to the RF group with conventional lesioning of the DRG at 67⁰C for 60 seconds versus no lesioning in the control group. At 8 weeks post operation, eight out of nine RF patients reported success, while two of 11 in the control group, defined as greater than 2- point reduction on the visual analog scale (VAS). This suggested short-term success where dyesthesia and hypoesthesia side effects were short lived (lasting <3 months).

There have been no prospective controlled trials on TRF of the thoracic DRG. **Stolker et al.** (Stolker et al., 1994) conducted a prospective uncontrolled trial using TRF of the thoracic DRG at 67 °C to treat 45 patients afflicted with thoracic segmental pain. They reported that 91% patients obtained > 50% pain relief at 2 months and that 78% continued to experience pain relief for 13 to 46 months. A smaller number of patients (13.3%) reported a transient burning pain in the corresponding dermatome that subsided within 3 weeks. In Neuropathic Pain their review, Malik and Benzon (Malik & Benzon, 2008) concluded that larger-scale, longer term, controlled clinical trials are required to clearly establish the efficacy of TRF-DRG for different types of neuropathic pain, particularly pain originating from thoracic DRG¹⁶. Although prospective observational and retrospective studies have yielded consistent support for DRG treatment in the cervical, thoracic, lumbar, and sacral regions , controlled studies are less compelling, complicated by the challenge of the lurking deafferentated pain potential. Further, patient selection appears to be vague in predicting treatment outcomes. Larger, sham-controlled, prospective studies are required to elucidate the place of TRF treatment of the DRG for treatment of chronic pain.

AIM OF THE WORK

To evaluate the effectiveness and safety of Pulsed and Thermal Radiofrequency lesion of the dorsal root ganglion (RF-DRG) on a consecutive group of patients presenting with chronic thoracic pain due to vertebral bone metastasis.

STUDY DESIGN

This is a Prospective Randomized Controlled trial that will be conducted at the National Cancer Institute. All patients who are eligible for the study will be included and randomized into 3 equal groups.

PATIENTS AND METHODS

After approval from the Ethics Committee at the National Cancer Institute, Cairo University, and obtaining written informed consent, eighty-one patients with thoracic segmental pain due to metastasis, unresponsive to conventional therapy and meeting the inclusion criteria will be randomly assigned to either one of the two types of treatment, PRF or TRF lesioning of the DRG or the control group. Patients will be carefully evaluated for neurologic deficits and side effects. Assessment of pain will be done at baseline then at 1, 3, 6 months after the procedure. Randomization will be done using randomized permuted block design. Randomization list will be generated through random.org online site.

INCLUSION CRITERIA:

1. A greater than 6-month history of segmental pain of thoracic vertebral body metastasis origin.

2. Unsatisfactory pain control with oral pharmacotherapy including strong opioid with VAS >5 .
3. Absence of a chronic or progressive motor deficit.
4. Absence of significant sensory deficit.
5. No indication for percutaneous or open surgical intervention.
6. Magnetic resonance imaging and Computed Tomography evidence of thoracic involvement.
7. ASA status of II to III .
8. Age \geq 18 .
9. Body mass index (BMI) :less than forty and more than twenty .
10. Informed consent

EXCLUSION CRITERIA:

1. Known sensitivity or contraindication to injected materials: local anesthetics.
2. History of psychological disorders.
3. Evidence of significant neurological deficit.
4. Inability to lie prone.
5. Local contraindication to procedure e.g. local sepsis at the site of intervention, coagulopathy.
6. Patient refusal.

Patients will be randomly assigned and divided into 3 equal comparable groups. Before the procedure, laboratory investigations, Dorsal X-ray, CT and MRI will be done. All Patients will be interviewed and examined by physicians trained in interventional pain management. Patients will be carefully assessed on physical exam for sensory, motor, or reflex deficit and

carefully documented. Patients will be informed about the technique of the blocks, and written informed consents will be obtained.

The types of measures used to assess pain relief will include single rating scales; VAS, and multiple-dimension composite measures; Oswestry Low Back Pain Disability Questionnaire (ODI), The European Organisation for Research and Treatment of Cancer (EORTC) QLQ-C30 and QLQ-BM22.

VAS; is commonly used to rate various subjective experiences a VAS is usually a horizontal line, 100 mm in length, anchored by word descriptors at each end such as "no pain" on the left and "severe pain" on the right, as illustrated in Fig. 1. The patient marks on the line three pain ratings, corresponding to current, best and worst intensity of pain experienced over the past 24 hours. The average of the 3 ratings will be used to represent the patient's level of pain over the previous 24 hours.. The VAS score is determined by measuring in millimeters from the left hand end of the line to the point that the patient marks.

[figure not shown]

Fig.(1) VAS, used in patients diary for guide in self-score pain.

The VAS has consistently demonstrated sensitivity to changes in cancer pain associated with treatment or time) and usually shows strong associations with other pain intensity ratings, it appears adequately valid and reliable as measures of pain intensity among the many different samples of persons with cancer ¹⁷.

ODI is a self-administered questionnaire divided into ten sections, each with six items designed to assess limitations of various activities of daily living. Each section is scored on a 0 to 5 scale, with 5 representing the greatest disability. The index is calculated by dividing

the summed score by the total possible score, which is then multiplied by 100 and expressed as a percentage. Thus, for every question not answered, the denominator is reduced by 5. If a patient marked more than one statement for a question, the highest scoring statement is recorded as the true indication of disability. It takes 3.5 to 5 minutes to complete the questionnaire and approximately 1 minute to score. The scores are assessed from 0% to 20% to indicate minimal disability, 20% to 40%, to indicate moderate disability, 40% to 60% to indicate severe disability, 60% to 80% to indicate crippled, and 80% to 100% to indicate bed bound or exaggerating their symptoms¹⁸. The ODI is the most commonly used disease specific patient reported outcome tool to measure functional disability related to back pain¹⁹.

When using only QOL tools as outcome measurement, the majority of cancer studies recommended CP (Cut point) 1–5 as mild pain, 6 as moderate pain, and 7–10 as severe pain²⁰. CPs is defined as the upper bound of a pain intensity category²¹ as shown in Fig. (2).

Table 1 CPs for cancer patients

Author, date and sample size	Pain site and type	Patient type	Pain measured	CPs
Serlin et al. [1995] (n=1,897) (10)	Metastatic cancer (non-specific origin)	Inpatient and outpatient	Worst pain	4, 6
Paul et al. [2005] (n=160) (19)	Metastatic cancer—bone metastases	Outpatient	Worst pain; average pain	4, 7; 4, 7
Chow et al. [2006] (n=217) (32)	Metastatic cancer—bone metastases	Outpatient	Not specified	4, 7
Li et al. [2007] (n=199) (18)	Metastatic cancer—bone metastases	Outpatient	Worst pain; average pain; current pain	4, 6; 4, 6; 2, 6
Given et al. [2008] (n=588) (33)	Solid tumors or non-Hodgkin's lymphoma	Outpatient	Average pain	1, 4
Kalyadina et al. [2008] (n=148) (25)	Cancer or advanced-stage hematological malignancy	Inpatient and outpatient	Worst pain	4, 6
Ferreira et al. [2011] (n=143) (17)	Cancer with pain	Outpatient	Worst pain	4, 7

CPs, cut points.

Fig. (2). Cut points for Cancer Patients.

EORTC has developed one of the most commonly used measurements for this purpose: the QLQ-C30 which is designed to capture QOL outcomes in a brief internationally recognized and validated tool²². EORTC QLQ-C30 (version 3), contains 15 relevant items to palliative care from the QLQ-C30, including multi-item physical and emotional function scales, multi-item symptom scales (fatigue and pain), single-item symptom scales (nausea/vomiting, appetite, dyspnea, insomnia, and constipation), and one scale pertaining to perceived overall

QOL. The EORTC **QLQ-BM22** is a sub-module of the QLQ-C30 and is an internationally recognized and validated scale used to measure QOL in bone metastases patients ²³. The QLQ-BM22, includes four subscales: painful sites, pain characteristics, functional interference, and psychosocial aspects. Both questionnaires use a 4-point Likert scale ranging from 1 (not at all) to 4 (very much) to rate each item, except for the final 2 question of the QLQ-C30 pertaining to overall QOL which is scored from 1 (very poor) to 7 (excellent). Each subscale is then linearly converted to a score from 0 to 100. For the QLQ-BM22, a higher score indicates worse symptom burden for painful sites and pain characteristics, and better functioning for functional interference and psychosocial aspects. For the QLQ-30, higher scores in the emotional, physical, and QOL scales indicate greater functioning and better ²¹.

VAS, ODI, QLQ-C30 and QLQ-BM22 will be used to evaluate pain, quality of life, and performance status before the procedure and at 3 days and 1, 3, 6 months after the procedure²⁴.

In the holding area, midazolam 0.02 mg/kg IV will be given after fixation of a 20 G cannula. All RF procedures will be performed in the hospital outpatient ambulatory care setting using local anesthesia and conscious sedation as necessary, with fluoroscopic guidance to facilitate needle placement. The segmental spinal levels treated will be selected based on the patients' pain referral pattern as determined by history and physical examination findings. After sterile skin preparation, RF will be performed with the patient in the prone position with mild flexion of the spine and the fluoroscopy beam positioned in an antero-posterior (AP) direction. A 10 cm RF needle 20 G with a 10 mm active tip. The image intensifier will be rotated in a cephalo-caudad direction until the endplates of the adjacent thoracic intervertebral discs is lined up and the transverse processes became discernable from the ribs. The needle is then inserted in a slightly medial-cephalad direction under the transverse processes, and using lateral fluoroscopic imaging, incrementally walking into the thoracic intervertebral foramen . The correct position of the needle's tip should be exactly in line with the facet joint spaces on the anteroposterior projection of the image intensifier, and in the posterior part of the foramen on the lateral projection. Once correct needle position is

confirmed by image and since neural tissue cannot be seen on plain radiographs and the DRG may vary with respect to its spatial relationship with the intervertebral foramen, so the location of the needle tip will confirmed not only by image but also by sensory stimulation at 50 Hz. The point of maximum stimulation is where sensory response in the painful dermatome can be elicited with stimuli below 0.5 V intensity and this is designated to be the location of the DRG. Slight redirection can be done to optimize the stimulation; injection of contrast reveals epidural uptake. After establishing the site for the RF, 1 ml 2% lidocaine should be injected through the needle. The needle is then connected to a RF generator (Baylis Medical com. Inc. Canada).

Group 1: Patients will receive PRF with temperature 42°C for 480 sec., 2 active cycles per second of 20 milliseconds each , with a voltage output 40 to 60-V range, impedance ranges between 150 and 400 Ohms at all levels using Fluoroscopic guidance (FG). The block will be done as that described by **Young-Chang P. et al** ⁸.

Group 2: Patients will receive TRF with temperature 80°C for 90 sec., 2 cycles, using FG . The block will be done as that described by **Ken-ichiro U** ¹⁶.

Group 3: The control group having identical needle placement and preparation without the RF lesioning (only local anesthetic).

OUTCOME AND ASSESSMENT

Primary outcome measure:

It will include:-

-VAS, ODI, QLQ-C30 and QLQ-BM22 to evaluate pain, quality of life, and performance status at 1, 3, 6 months after the procedure.

Secondary outcome measures:

It will include :-

- Neurological defects .
- Dysthesia and hypoesthesia.
- Change in physical activities, and analgesic use.
- Any other complication from either the technique as pneumothorax or local anesthetic, anesthesia dolorosa and burning pain.
- Patients' satisfaction with analgesia through a phone call a week after procedure on 5-level likert scale, (not satisfied at all, only slightly satisfied, somewhat or partly satisfied, very satisfied, perfectly satisfied)

STATISTICS

1 - Sample size estimation:

According to studies ^(13,15,16) , to see a significant reduction in VAS defined as at least 50% reduction, ODI, QLQ-C30 and QLQ-BM22 score ($P < 0.01$) with a background standard deviation of 1.0, significance level of 0.05 and power of a test of 80%, minimum number of patients needed would be 25 per group. Because difference in VAS , ODI, QLQ-C30 and QLQ-BM22 score will be more evidenced with control group, the number needed would be much smaller , so the total number needed in the present study would be 69 patients that will be randomized into 3 equal groups. For non-parametric correction, we increased the number to 27 patients for each group.

2- Statistical analysis plan:

Data will be analyzed using SPSS version 18.0. Numerical data will be presented as mean, standard deviation or median and range as appropriate. Categorical data will be presented as numbers and proportions. Mixed models ANOVA will be used to show effect of time on pain score and also to evaluate group interaction. Non-parametric tests ; Friedman's test will be used if data did not show normal distribution. Significance level will be considered at 0.05.

REFERENCES

1. **Smith HS.** and **Barkin RL**, Painful boney metastases, American Journal of Therapeutics , 2014 ;21(2):106-130.
2. **Patrick W.**, Bone Cancer Pain: From Mechanism to Therapy, Current opinion in supportive and palliative care 2014 ; 8(2): 83–90.
4. **Bhatia A.** , Questions Regarding "Pulsed Radiofrequency for Chronic Intractable Lumbosacral Radicular Pain: A Six-Month Cohort Study", Pain Medicine 2016; 17(5):989.
6. **R. Carter W. Jones III**, Neuroinflammatory effects of Radiofrequency, European Journal of Pain 2014; 18 :149-150.
7. **Zeldin A. and Ioscovich A.**, Pulsed Radiofrequency for Metastatic Pain Treatment, Pain Physician 2008; 11:921-922 .

8. **Young-Chang P. Arai, Makoto N., Yoshihiro Y., Maki A., Miki K., Chiharu S., Akiko K., Kazuyo K., and Tatsunori I.,** Dorsal Root Ganglion Pulsed Radiofrequency for the Management of Intractable Vertebral Metastatic Pain: A Case Series, *Pain Medicine* 2015; 16:1007 – 1012.

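### The order of consent, eligibility checks and randomisation is unclear and partly conflicting, which leaves room for refusals and exclusions made with the arm known

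*Combined protocol and SAP*

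**What the plan says.** The Combined protocol and SAP touches on the sequence in three places.

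- STUDY DESIGN: "All patients who are eligible for the study will be included and randomized into 3 equal groups".
- PATIENTS AND METHODS, opening paragraph: after ethics approval and "obtaining written informed consent, eighty-one patients with thoracic segmental pain due to metastasis", those who are "unresponsive to conventional therapy and meeting the inclusion criteria will be randomly assigned to either one of the two types of treatment" or to control. This sentence names the inclusion criteria but not the exclusion criteria.
- PATIENTS AND METHODS, the paragraph after EXCLUSION CRITERIA: "Patients will be randomly assigned and divided into 3 equal comparable groups. Before the procedure, laboratory investigations, Dorsal X-ray, CT and MRI". It continues with an interview and a documented neurological examination, and ends: "Patients will be informed about the technique of the blocks, and written informed consents will be obtained".

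On the mechanics of randomisation, the plan gives permuted blocks and a list generated on random.org. On the procedure, it gives one description of needle placement, stimulation and lidocaine for everyone, and defines Group 3 as "The control group having identical needle placement and preparation without the RF lesioning".

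**The concern.** The last of the three paragraphs lists the work-up and consent after the assignment sentence, and much of that work-up settles whether a patient belongs in the trial. A site that took the paragraph as its running order would learn the arm first, then examine the patient, read the imaging and ask for consent.

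The three arms differ in kind: a thermal lesion, a pulsed treatment, and local anaesthetic alone. A patient told of a control allocation might decline. An examiner might judge a borderline sensory finding more strictly in a patient due for a thermal lesion. If losses of this kind differ between arms, the groups analysed are no longer the groups that randomisation created, and later adjustment cannot reliably repair that.

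**Working it through.** No arithmetic applies, so the check is a comparison of the texts in four steps.

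**1. Do the later steps decide eligibility?** Set against the numbered criteria:

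| Step written after the assignment sentence | Criterion it bears on | Time point given |
|---|---|---|
| Laboratory tests | Exclusion 5 (coagulopathy); the tests are not named, so this link is an inference | Before the procedure |
| CT and MRI | Inclusion 6 | Before the procedure |
| Sensory, motor and reflex examination | Inclusion 3 and 4, exclusion 3 | None |
| Written consent | Inclusion 10, exclusion 6 (refusal) | None |

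Most of them do. Inclusion 4 and exclusion 3 turn on whether a deficit is significant, a term the plan does not define, so they leave room for judgement.

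**2. Do the three statements agree on order?**

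- STUDY DESIGN: eligible, then randomised.
- Opening methods paragraph: consented and meeting the inclusion criteria, then assigned.
- Paragraph after EXCLUSION CRITERIA: assigned, then tests, examination and consent, if sentence order is read as time order.

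For the tests, the third statement can be squared with the other two, because work done before the procedure may also have been done before randomisation. For consent the tension is sharper. The opening paragraph has it obtained before assignment; the later one mentions it again, in the future tense, after assignment and without a time point. The text does not say whether this is the same consent or a second one.

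**3. Does another part of the plan close the gap?** The randomisation text gives no block size, no holder of the list and no concealment method. STATISTICS defines no analysis population and no rule for a patient found ineligible after assignment. No statement says who in this trial is blinded. Nothing written would stop a patient being dropped after assignment, or say how such a patient is counted.

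**4. At what point do the arms first differ?** Placement, stimulation and the lidocaine injection are common to all patients. The groups diverge only when the needle is connected to the generator and a lesion is or is not made. The plan therefore needs nobody to know the arm before then.

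**The case against.** The strongest reply is that the plan states the order explicitly twice, correctly both times, and that eligible in STUDY DESIGN naturally covers the exclusion criteria as well. The later paragraph never says that the checks follow randomisation. The document is also not written in time order: it sets out the follow-up assessments, from 3 days to 6 months, before it describes the holding area and the procedure. The neurological examination may be baseline recording, since neurological defects and sensory changes are secondary outcomes. No exclusion after assignment is described anywhere, and nothing says that examiners or patients know the arm at that stage.

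Much of this stands, and it rules out three stronger readings.

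- A reader might infer that the plan flatly contradicts itself. For the tests it does not, because their only time anchor fits either order. The conflict is clearest on consent.
- A reader might treat the stimulation response as a technical eligibility test that is known only at the procedure. The plan uses it to find the target, the spot at which "sensory response in the painful dermatome can be elicited with stimuli below 0.5 V intensity and this is designated to be the location of the" ganglion, and slight redirection is allowed. It is not among the eligibility criteria. What is missing is a statement of how a patient is counted if the response is not obtained.
- A reader might infer that late exclusions would take the trial below its required size. The documents give no rate of such losses. STATISTICS also offers no single floor: it gives a minimum of 25 per group, then a total of 69 (69 / 3 = 23 per group), then 27 per group (3 × 27 = 81).

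The reply does not dispose of the point. An examination can serve as baseline and as an eligibility check at once, the second mention of consent remains unexplained, and the missing concealment and analysis rules mean that a site following the later paragraph would breach nothing in writing.

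**Conclusion.** The concern holds as an unclear and partly conflicting sequence that should be reconciled. The risk is selection bias from refusals and suitability judgements made with the arm known. It is inferred and rests on two assumptions: that the later paragraph is followed in the order written, and that the allocation is known to the patient or the examiner once assigned. The documents confirm neither and exclude neither. The size of any bias depends on how unevenly losses would fall across the arms, and no figure in the documents allows a calculation. The point still merits a change, because the design itself permits a nearly free safeguard.

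**What to change.** 1. Reconcile the paragraphs. State that written consent, laboratory tests, X-ray, CT, MRI, neurological examination and every inclusion and exclusion criterion are completed and recorded before a patient is randomised.
2. Keep the allocation concealed, with a named holder of the list, and open it only once needle position is confirmed, just before connection to the generator. The opening is the moment of randomisation.
3. Define the analysis population as everyone whose allocation has been opened, each analysed in the assigned arm. Report any later withdrawal by arm, with the reason.

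The cost is a few sentences of protocol text and a sealed allocation handled in the procedure room. A patient in whom placement fails is not randomised and may need replacing to reach 81, and will have had sedation and needle insertion without entering the comparison. No extra visits or tests are needed.

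The title page records recruitment as completed on 30 July 2018. For the trial as run, the sponsor can still state the order actually used, report exclusions and refusals after assignment by arm, and analyse all assigned patients in their assigned arms.

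### The plan disagrees with itself on a 3-day assessment, and the mixed ANOVA does not say which visits it uses, so its group and interaction tests depend on the schedule followed

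*Combined protocol and SAP*

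**What the plan says.** Three places in the protocol set assessment times.

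- Patients and Methods, opening paragraph: "Assessment of pain will be done at baseline then at 1, 3, 6 months after the procedure".
- Patients and Methods, end of the description of the outcome instruments: VAS, ODI, QLQ-C30 and QLQ-BM22 are used "before the procedure and at 3 days and 1, 3, 6 months after the procedure".
- Outcome and Assessment, primary outcome: the same four instruments are used "to evaluate pain, quality of life, and performance status at 1, 3, 6 months after the procedure".

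The secondary outcomes do not list a 3-day reading.

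The statistical analysis plan (Statistics, item 2) says "Mixed models ANOVA will be used to show effect of time on pain score and also to evaluate group interaction". For non-normal data, "Friedman's test will be used if data did not show normal distribution". It does not list the levels of time, say whether baseline is one of them, or give a 3-day value any role.

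**The concern.** The first two statements describe the same pain assessment with different visits. The third settles which visits are primary, but the analysis plan does not refer to it. A repeated-measures ANOVA is defined by its levels of time: they fix the degrees of freedom, the weight each visit carries in the group effect, and the pattern that the interaction tests. Friedman's test, with degrees of freedom one fewer than the number of visits, depends on the same list.

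An analyst could follow the written plan and either include or leave out a 3-day reading after seeing the results. If it is included, the group and interaction tests no longer answer the question that the primary outcome poses.

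**Working it through.** **1. Levels and degrees of freedom.** Inputs are 3 arms of 27, so 81 patients (Statistics, item 1). With T levels of time, the time effect has T − 1 df, the group-by-time interaction 2(T − 1), and the within-patient error 78(T − 1).

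| Visits entered | T | Time df | Interaction df | Error df |
|---|---|---|---|---|
| Baseline, 1, 3, 6 months (opening of Patients and Methods) | 4 | 3 | 6 | 234 |
| Baseline, 3 days, 1, 3, 6 months (instrument description) | 5 | 4 | 8 | 312 |
| 1, 3, 6 months only (primary outcome) | 3 | 2 | 4 | 156 |

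**2. Assumptions for the size.** The plan gives no difference in scale units and no correlation between visits. I assume a difference from control of 1.2 at each of months 1, 3 and 6, none at baseline, correlation 0.5 between visits, and two-sided alpha 0.05. The 3-day difference is varied. The SD is 1.0 (the only one in the plan) or 2 (my assumption).

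**3. Two-arm comparison of the post-procedure average.** The mean of k visits has variance SD²(1 + (k − 1)ρ)/k. The standard error of the difference is √(2 × variance/27), and the t-test has 52 df.

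- Without day 3 (k = 3): the estimate is 1.2. At SD 2 the variance is 4 × 2/3 = 2.667, the standard error 0.444, the ratio 2.70 and the power 75%.
- With day 3 (k = 4) and no 3-day difference: the estimate is (0 + 3 × 1.2)/4 = 0.9. At SD 2 the variance is 4 × 2.5/4 = 2.5, the standard error 0.430, the ratio 2.09 and the power 54%.
- With 3-day differences of 0.5 or 1.5 the estimates are 1.025 and 1.275, and power at SD 2 is 65% and 83%.
- At SD 1.0 the first two ratios double to 5.40 and 4.18. Power is over 99.9% without day 3 and 98% with it.
- At SD 2 and no 3-day difference, correlation 0.3 gives 84% falling to 65%, and correlation 0.7 gives 68% falling to 45%.

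**4. Interaction test.** Both active arms are taken to differ from control by the same amount d(t), with sphericity. The non-centrality is 27 × (2/3) × Σ(d(t) − mean d)² / (SD²(1 − ρ)). At SD 2 this is 9 × Σ(d(t) − mean d)².

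| Levels | 3-day difference | Sum of squares | Non-centrality | Power |
|---|---|---|---|---|
| 4 | not included | 1.080 | 9.72 | 62% |
| 5 | 0 | 1.728 | 15.55 | 80% |
| 5 | 0.5 | 1.208 | 10.87 | 62% |
| 5 | 1.2 | 1.152 | 10.37 | 59% |
| 5 | 1.5 | 1.368 | 12.31 | 69% |

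If only months 1, 3 and 6 enter, a constant difference of 1.2 makes the sum of squares zero. The interaction test then has power equal to its 5% alpha, although the arms differ at every primary visit.

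**5. Baseline as a level or as a covariate.** At SD 2, entering baseline as a fourth level alongside months 1, 3 and 6 gives a two-arm group effect of (0 + 3.6)/4 = 0.9 with variance 2.5, so 54% power again. With baseline as covariate, the estimate stays at 1.2 and the variance is 2.667 − 4 × 0.5² = 1.667. The standard error is 0.351, the ratio 3.42 and the power about 92%.

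**The case against.** The best defence is that the primary outcome is already limited to months 1, 3 and 6, and that collecting a further early reading is compatible with that. This stands in part. The instrument schedule and the primary outcome do not conflict; the contradiction is between the two schedules inside Patients and Methods. What remains is that the analysis plan does not tie its ANOVA to the primary visits. Comparisons at a single month would be little affected, but the plan specifies none.

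It is also fair to say that the two-arm averaged comparison in the working is not an analysis that the plan names. The plan names a time effect and a group interaction. The comparison only illustrates how an added visit shifts a group difference. At the plan's own SD of 1.0 and the assumed difference, the loss nearly disappears.

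Three stronger readings do not hold:

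- A reader might infer that more interaction degrees of freedom must cost power. That would follow only if the non-centrality stayed fixed. It changes with the added visit and can rise enough to increase power, as in the case with no 3-day difference.
- A reader might infer that a 3-day visit always dilutes the group effect. It does so only if the 3-day difference is smaller than the later ones.
- Every arm has "1 ml 2% lidocaine should be injected through the needle", and a reader might infer that the 3-day value therefore measures something different. The documents give no duration for its effect, and an additive effect common to all arms cancels in the between-arm difference.

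**Conclusion.** The contradiction is in the current text, and it reaches the analysis because the ANOVA and its Friedman fallback are tied to none of the three lists of visits. The interaction has 6, 8 or 4 degrees of freedom depending on the list followed. The certain part is this freedom to choose after the data are seen.

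The numerical consequence is conditional on the assumed difference, SD and correlation, and ranges from negligible to substantial. The loss in the averaged comparison is about 21 percentage points at SD 2 with no 3-day difference, and under 2 points at SD 1.0. At SD 2 the interaction test can gain or lose from the same added visit, with power between 59% and 80% against 62% without it. The documents therefore support neither a fixed loss of power nor a fixed direction. The point should be corrected, but it does not by itself invalidate the trial.

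**What to change.** 1. Reconcile the two schedules in Patients and Methods with each other and with the primary outcome, so that the protocol says once whether a 3-day assessment is made.
2. State in the statistical analysis plan that the primary between-arm comparison uses months 1, 3 and 6 only, with the baseline value as covariate and not as a level of time. Name the between-arm effect as the primary test, because an interaction over those three visits alone would miss a constant difference.
3. Report any 3-day value separately as an early secondary outcome.
4. List the visits for the Friedman fallback in the same way.

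This costs protocol and analysis-plan wording only. Baseline is already collected, and no 3-day data are discarded. The cover page closes recruitment on 30 July 2018, so six-month visits would run to about the end of January 2019, before the document date of 31 March 2019. If the data have already been examined, date the change and give the results with and without the 3-day visit.
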